## 8.1 Efficacy assessments

This study will evaluate the primary endpoint of PFS. Secondary endpoints include DoR, ORR, OS, OS18, and PFS6. Efficacy assessments of PFS, PFS6, DoR, and ORR will be derived (by AstraZeneca) using Investigator assessments according to RECIST 1.1.

Tumor assessments utilize images from CT (preferred) or MRI, each preferably with IV contrast, of the chest, abdomen, and pelvis, collected during screening/baseline and at regular (follow-up) intervals during study treatment. Any other areas of disease involvement should be additionally imaged based on the signs and symptoms of individual patients.

The RECIST 1.1 guidelines ([Appendix F](#)) provide a method of assessment of change in tumor burden in response to treatment. Screening/Baseline imaging should be performed no more than 28 days before start of study treatment, and ideally should be performed as close as possible to and prior to the start of study treatment. The RECIST 1.1 assessments of baseline images identify TLs (defined measurable) and non-target lesion (NTLs). On-study images are evaluated for TLs and NTLs chosen at baseline and for new lesions when they appear. This allows determination of follow-up TL response, NTL response, and overall timepoint tumor responses (CR, PR, SD, PD, or not evaluable [NE]).

Radiologic efficacy for all patients (both treatment arms) will be assessed on images collected q8w  $\pm$ 1 week for the first 48 weeks relative to the date of randomization and q12w  $\pm$ 1 week thereafter until RECIST 1.1-defined objective disease progression or off-study. The assessment schedule must be followed regardless of any delays in dosing (refer to [Table 1](#)). If an unscheduled assessment is performed and the patient has not progressed, every attempt should be made to perform the subsequent assessments at his/her next regularly scheduled imaging visit. Assessments of tumor response (CR, PR, or SD) must be confirmed at the next (and no later than the next) scheduled imaging visit, and no less than 4 weeks and no more than 8 weeks after the prior assessment.

### 8.1.1 Central reading of scans

All images, including unscheduled visit scans, will be collected on an ongoing basis and sent to an AstraZeneca-appointed Contract Research Organization for quality control and storage. A BICR of images will be performed at the discretion of AstraZeneca. Results of these independent reviews will not be communicated to Investigators, and results of Investigator RECIST 1.1 assessments will not be shared with the central reviewers. The management of patients will be based in part on the results of the RECIST 1.1 assessment conducted by the Investigator.

### 8.1.2 Tumor biopsies

After obtaining informed consent, patient tumor samples will be screened for HRR mutation during the screening phase by a central laboratory (details of HRR mutation assessment follow below and in the laboratory manual).

All patients must provide an FFPE tumor sample for tissue-based HRR gene panel mutation testing. The analysis will be performed at a central laboratory testing service using the DNA extracted from FFPE tissue. Tumor tissue can be either from the primary tumor or metastatic biopsy. Samples should not be collected specifically for this study but should be obtained as part of patients' routine clinical care. Archived tumor specimens are acceptable for HRR testing. The tumor sample will be tested for loss of function and alterations in 15 pre-specified HRR genes: *ATM*, *BRCA1*, *BRCA2*, *BARD1*, *BRIP1*, *CDK12*, *CHEK1*, *CHEK2*, *FANCL*, *PALB2*, *PPP2R2A*, *RAD51B*, *RAD51C*, *RAD51D*, and *RAD54L*. If the test results indicate that the patient has at least 1 qualifying mutation in any of these genes, the patient will be considered HRRm for the purposes of the study. Patients with a prior test result from an HRR testing laboratory panel will not have to wait for HRR testing completion to determine their biomarker status, if they provide permission for reanalysis of their data at an HRR testing laboratory (see laboratory manual for further details); however, an FFPE tumor sample is still mandatory for central confirmatory testing and exploratory biomarkers analysis. No local testing results are permitted for eligibility purposes. All tumor samples will be analyzed for a range of cancer-related genes to explore correlations between clinical response and DNA alterations. Full genetic testing results from the central laboratory testing service will be provided to the Investigator upon individual request for patients that fail screening or for treated patients upon disease progression and treatment discontinuation.

Tumor lesions used for newly acquired biopsies should not be RECIST 1.1 TLs, unless there are no other lesions suitable for biopsy. Samples with limited tumor content and fine-needle aspirate specimens are not acceptable. Specimens from metastatic bone lesions are typically unacceptable unless there is a significant soft tissue component and should not be decalcified.

### 8.1.3 Survival assessments

Assessments for survival must be made every 2 months following treatment discontinuation. Survival information may be obtained via telephone contact with the patient or the patient's family or by contact with the patient's current physician. The details of first and subsequent therapies for cancer, after discontinuation of treatment, will be collected.

In addition, patients on treatment or in survival follow-up will be contacted following the DCO for the primary analysis and all subsequent survival analyses to provide complete survival data. These contacts should generally occur within 7 days of the DCO.

#### **8.1.4 Clinical outcome assessments**

Patient Reported Outcome (PRO) is an umbrella term referring to all outcomes and symptoms that are directly reported by the patient. In addition to assessing clinical endpoints in oncology clinical trials, it is important to assess treatment impact on disease-related symptoms and health-related quality of life (HRQoL) of the patient to aid in characterizing treatment benefit to overall wellbeing and in making risk-benefit evaluations. Moreover, PROs assist in the documentation of symptoms and specifically what symptoms and impacts are most important to patients and how these relate to clinical outcomes. The following PROs will be administered in this study: The European Organisation for Research and Treatment of Cancer 30-item core quality of life questionnaire (EORTC QLQ-C30), 5-level health state utility index (EQ-5D-5L), Patient Global Impression of Change (PGIC), and the Vulnerability Elders Survey-13 (VES-13) (see [Appendix G](#)). The VES-13 will only be given at baseline to assess the patient's frailty and not to assess the efficacy of treatment (see Section 8.2.6).

##### **8.1.4.1 EORTC QLQ-C30**

The impact of treatment and disease state on symptoms and HRQoL will be assessed using the EORTC QLQ-C30, a 30-item self-administered questionnaire (see [Appendix G](#)). The rationale for selecting the EORTC QLQ-C30 is primarily because it has a good coverage of general cancer symptoms and impact concepts. The questionnaire consists of 9 multiple-item scales: 5 scales that assess aspects of functioning (physical, role, cognitive, emotional, and social), 3 symptom scales (fatigue, pain, and nausea and vomiting), and a global health status/Quality of Life (QoL) scale. In addition, there are 5 single-item measures assessing additional symptoms commonly reported by cancer patients (dyspnea, loss of appetite, insomnia, constipation, and diarrhea) and a single item concerning the perceived financial impact of the disease. All but 2 questions have 4-point scales: "Not at all," "A little," "Quite a bit," and "Very much." The 2 questions concerning global health status and QoL have 7-point scales with ratings ranging from "Very poor" to "Excellent." For each of the 15 domains (9 multiple-item scales and 6 single-item scales), final scores are transformed such that they range from 0 to 100, where higher scores indicate greater functioning, greater QoL, or greater level of symptoms ([Aronson et al 1993](#)).

#### **8.1.4.2 EQ-5D-5L**

The EuroQoL 5-Dimension (EQ-5D) is a standardized measure of health status developed by the EuroQoL Group in order to provide a simple, generic measure of health for clinical and economic appraisal ([EuroQoL Group 1990](#)). Applicable to a wide range of health conditions and treatments, it provides a simple descriptive profile and a single index value for health status that can be used in the clinical and economic evaluation of health care as well as in population health surveys. The questionnaire assesses 5 dimensions as follows: mobility, self-care, usual activities, pain/discomfort, and anxiety/depression. Each dimension has 5 response options (“no problems,” “slight problems,” “moderate problems,” “severe problems,” and “extreme problems”) that reflect increasing levels of difficulty ([EuroQoL Group 2013](#)).

Since 2009, the EuroQoL Group has been developing a more sensitive version of the EQ-5D (the EQ-5D-5L) that expands the range of responses to each dimension from 3 to 5 levels of increasing severity ([Herdman et al 2011](#)). Preliminary studies indicate that the 5L version improves upon the properties of the 3L measure in terms of reduced ceiling effect, increased reliability, and an improved ability to differentiate between different levels of health ([Janssen et al 2008a](#), [Janssen et al 2008b](#), [Pickard et al 2007](#)).

The patient will be asked to indicate his/her current health state by selecting the most appropriate level in each of the 5 dimensions. The questionnaire also includes a visual analog scale, where the patient will be asked to rate current health status on a scale of 0 to 100, with 0 being the worst imaginable health state.

#### **8.1.4.3 PGIC**

The PGIC item is included to assess how a patient perceives overall change in health status since the start of study treatment (see [Appendix G](#)). Patients will be asked “Overall, how would you rate the change in your bladder cancer symptoms since you started this study?” and will choose from 7 response options of “very much improved” to “very much worse.”

#### **8.1.4.4 Administration of patient-reported outcomes questionnaires**

Patients will perform the PRO assessments using an electronic tablet (ePRO) during clinic visits and will take approximately 15 minutes to complete. Note that the VES-13 will be performed at baseline and will not be performed at subsequent clinic visits.

Each site must allocate the responsibility for the administration of the PRO instruments to a specific individual (eg, a research nurse or study coordinator) and, if possible, assign a back-up person to cover if that individual is absent. The PRO questionnaires must be administered and completed at the clinic as per the SoAs ([Table 1](#) and [Table 2](#)).

It is important that the site staff explains the value and relevance of PRO data to hear directly from patients how they feel. The following best practice guidelines should be followed:

- It is preferred that PRO questionnaires are completed prior to any other study procedures (following informed consent) and before discussion of disease progression to avoid biasing the patient's responses to the questions.
- PRO questionnaires must be completed in private by the patient.
- Patients should be given sufficient time to complete the PRO questionnaires at their own speed.
- The research nurse or appointed site staff should stress that the information is confidential. Therefore, if the patient has any medical problems, he/she should discuss them with the doctor or research nurse separately from the ePRO assessment.
- The research nurse or appointed site staff must train the patient on how to use the ePRO device using the materials and training provided in the ePRO device.
- The research nurse or appointed site staff must remind patients that there are no right or wrong answers and avoid introducing bias by not clarifying items. The patient should not receive help from relatives, friends, or clinic staff to answer the PRO questionnaires.

A key aspect of study success is to have high PRO compliance. Therefore, it is essential to follow SoA and that sites make sure the device is charged and fully functional at all times in order to minimize missing data.

## **8.2 Safety assessments**

Planned timepoints for all safety assessments are provided in the SoA.

### **8.2.1 Clinical safety laboratory assessments**

Blood and urine samples for determination of clinical chemistry, hematology, and urinalysis will be taken at the times indicated in the assessment schedules and as clinically indicated (see [Table 1](#) and [Table 2](#)).

Clinical laboratory safety tests, including serum pregnancy tests, will be performed in a licensed clinical laboratory according to local standard procedures. Sample tubes and sample sizes may vary depending on the laboratory method used and the routine practice at the site. Urine pregnancy tests may be performed at the site using a licensed test (urine or serum pregnancy test). Abnormal clinically significant laboratory results should be repeated as soon as possible (preferably within 24 to 48 hours).

Additional safety samples may be collected if clinically indicated at the discretion of the Investigator. The date, time of collection, and results (values, units, and reference ranges) will be recorded on the appropriate eCRF.

The Investigator should make an assessment of the available results with regard to clinically relevant abnormalities. The laboratory results should be signed and dated and retained at the site as source data for laboratory variables.

For information on how AEs based on laboratory tests should be recorded and reported, see Section 8.3.7.

The laboratory variables measured are presented in Table 9 (clinical chemistry), Table 10 (hematology), and Table 11 (urinalysis).

Other safety tests to be performed at screening include assessment for HBsAg, HCV antibodies, and HIV antibodies.

The following laboratory variables will be measured:

**Table 9 Clinical chemistry**

Albumin	Lipase b
Alkaline phosphatase a	Magnesium c
ALT a	Potassium
Amylase b	Sodium
AST a	Total bilirubin a
Bicarbonate c	Total protein
Calcium	TSH c
Chloride c	T3 free f (reflex)
Creatinine clearance d	T4 free f (reflex)

Gamma glutamyltransferase c	Urea or blood urea nitrogen, depending on local practice
Glucose	
Lactate dehydrogenase	

- a Tests for ALT, AST, alkaline phosphatase, and total bilirubin must be conducted and assessed concurrently. If total bilirubin is  $\geq 2\times$  upper limit of normal (and no evidence of Gilbert’s syndrome), then fractionate into direct and indirect bilirubin.
- b It is preferable that both amylase and lipase parameters are assessed. For sites where only 1 of these parameters is routinely measured, then either lipase or amylase is acceptable.
- c Bicarbonate (where available), chloride, creatinine clearance, gamma glutamyltransferase, and magnesium testing is to be performed at baseline, on Day 0 (unless all screening laboratory clinical chemistry assessments are performed within 3 days prior to Day 0), and if clinically indicated.
- d Creatinine clearance will be calculated by data management using Cockcroft-Gault (using actual body weight).
- e If TSH is measured within 14 days prior to Day 1 (first infusion day), it does not need to be repeated at Day 1.
- f Free T3 or free T4 will only be measured if TSH is abnormal or if there is a clinical suspicion of an AE related to the endocrine system.
- ALT Alanine aminotransferase; AST Aspartate aminotransferase, T3 Triiodothyronine; T4 Thyroxine; TSH Thyroid stimulating hormone.

**Table 10 Hematology**

Absolute lymphocyte count a	Hemoglobin
Absolute neutrophil count	Platelet count
Total white cell count	

a Can be recorded as absolute counts or as percentages.

Note: For coagulation parameters, activated partial thromboplastin time and international normalized ratio are to be assessed at baseline and as clinically indicated.

**Table 11 Urinalysis**

Bilirubin	Ketones
Blood	pH
Color and appearance	Protein
Glucose	Specific gravity

Note: Microscopy should be used as appropriate to investigate white blood cells and use the high power field for red blood cells. Urinalysis should be done at baseline (screening) and then as clinically indicated.

If a patient shows an AST or ALT  $\geq 3 \times$  ULN together with TBL  $\geq 2 \times$  ULN, refer to [Appendix E](#) for further instructions on cases of increases in liver biochemistry and evaluation of Hy's law. These cases should be reported as SAEs if, after evaluation, they meet the criteria for a Hy's law case or if any of the individual liver test parameters fulfill any of the SAE criteria.

All patients should have further hematology and chemistry profiles performed at 30 days ( $\pm 3$  days), 2 months ( $\pm 1$  week), and 3 months ( $\pm 1$  week) after permanent discontinuation of the IP (see [Table 2](#)).

Any clinically significant abnormal laboratory values should be repeated as clinically indicated and recorded on the eCRF. Situations in which laboratory safety results should be reported as AEs are described in Section [8.3.7](#).

All patients with Grade 3 or 4 laboratory values at the time of completion or discontinuation from the IP must have further tests performed until the laboratory values have returned to Grade 1 or 2, unless these values are not likely to improve because of the underlying disease.

### **8.2.2 Physical examinations**

Physical examinations will be performed according to the assessment schedules (see [Table 1](#) and [Table 2](#)). Full physical examinations will include assessments of the head, eyes, ears, nose, and throat and the respiratory, cardiovascular, GI, urogenital, musculoskeletal, neurological, dermatological, hematologic/lymphatic, and endocrine systems. Height will be measured at screening only. Targeted physical examinations are to be utilized by the Investigator on the basis of clinical observations and symptomatology. Situations in which physical examination results should be reported as AEs are described in Section [8.3.7](#).

### **8.2.3 Vital signs**

Vital signs (blood pressure [BP], pulse, temperature, and respiratory rate) will be evaluated according to the assessment schedules (see [Table 1](#) and [Table 2](#)). Body weight is also recorded at each visit along with vital signs. The following timepoints for vital signs assessments apply to infusions of durvalumab.

### **First infusion**

On the first infusion day, patients in the durvalumab + olaparib and durvalumab + placebo groups will be monitored, and vital signs will be collected/recorded in the eCRF prior to, during, and after infusion of IP as presented in the bulleted list below.

BP and pulse will be collected from patients before, during, and after each infusion at the following times (based on a 60-minute infusion):

- Prior to the beginning of the infusion (measured once from approximately 30 minutes before up to 0 minute [ie, the beginning of the infusion]).
- Approximately 30 minutes during the infusion (**halfway** through infusion).
- At the end of the infusion (approximately 60 minutes $\pm$ 5 minutes).

If the infusion takes longer than 60 minutes, then BP and pulse measurements should follow the principles as described above or be taken more frequently if clinically indicated. A 1-hour observation period is recommended after the first infusion of durvalumab. Additional monitoring with assessment of vital signs will be at the discretion of the Investigator per standard clinical practice or as clinically indicated.

### **Subsequent infusions**

BP, pulse, and other vital signs should be measured and collected/recorded in the eCRF prior to the start of the infusion. Patients should be carefully monitored, and BP and other vital signs should be measured during and after infusion as per institution standard and as clinically indicated. Any clinically significant changes in vital signs should be entered onto an unscheduled vital signs eCRF page.

Situations in which vital signs results should be reported as AEs are described in Section [8.3.6](#). For any AEs of infusion reactions, please enter the vital signs values into the eCRF.

#### **8.2.4 Electrocardiograms**

Resting 12-lead electrocardiograms (ECGs) will be recorded at screening and as clinically indicated throughout the study (see [Table 1](#)). ECGs should be obtained after the patient has been in a supine position for 5 minutes and recorded while the patient remains in that position.

Any clinically significant abnormalities detected require triplicate ECG results, including a QT interval corrected for heart rate using Fridericia's formula (QTcF) value >470 ms, 2 additional 12-lead ECGs should be obtained over a brief period (eg, 30 minutes) to confirm the finding.

Situations in which ECG results should be reported as AEs are described in Section [8.3.7](#).

#### **8.2.5 WHO/ECOG performance status**

WHO/ECOG performance status will be assessed at the times specified in the [Table 1](#) and [Table 2](#) based on the following:

- 0 Fully active; able to carry out all usual activities without restrictions
- 1 Restricted in strenuous activity, but ambulatory and able to carry out light work or work of a sedentary nature (eg, light housework or office work)
- 2 Ambulatory and capable of self-care, but unable to carry out any work activities; up and about more than 50% of waking hours
- 3 Capable of only limited self-care; confined to bed or chair more than 50% of waking hours
- 4 Completely disabled, unable to carry out any self-care, and totally confined to bed or chair

Any significant change from baseline or screening must be reported as an AE.

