**Table 2 Schedule of assessments for patients who have discontinued all study treatment**

Evaluation	Time since last dose of IP								For details, see Section
	Day ( $\pm 3$ )	Months ( $\pm 1$ week)						12 months and every 2 months thereafter ( $\pm 2$ weeks)	
	30	2	3	4	6	8	10		
Physical examination (full)	X								8.2.2
Vital signs (temperature, respiratory rate, blood pressure, and pulse)	X								8.2.3
Weight	X	X	X		X				8.2.3
Pregnancy test a	X	As clinically indicated							5.1
AE/SAE assessment	X	X	X						8.3
Concomitant medications	X	X	X						6.6
WHO/ECOG performance status	At timepoints consistent with tumor assessments; at 30, 60, and 90 days; and then at initiation of subsequent anticancer therapy b								8.2.5
Subsequent anticancer therapy c	<----->								8.1
Survival status d		X	X	X	X	X	X	X (every 2 months)	8.1
Hematology	X	X	X						Table 10
Clinical chemistry	X	X	X						Table 9
Urinalysis e	As clinically indicated								Table 11
TSH (reflex free T3 or free T4) f	X	X	X						Table 9
Durvalumab PK sample (serum) g			X						8.5.1.1
Olaparib PK sample (plasma)	X								8.5.1.2
Immunogenicity assessment (ADA sampling) to identify ADA responses g			X		X				8.5.2
Whole blood – exploratory analysis (mandatory) h			X						8.8.1.3

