### **8.3.7 Adverse events based on examinations and tests**

The results from the protocol-mandated laboratory tests and vital signs will be summarized in the clinical study report (CSR). Deterioration as compared to baseline in protocol-mandated laboratory values, and vital signs should therefore only be reported as AEs if they fulfil any of the SAE criteria or are the reason for discontinuation of treatment with an IP.

If deterioration in a laboratory value/vital sign is associated with clinical signs and symptoms, the sign or symptom will be reported as an AE, and the associated laboratory result/vital sign will be considered as additional information. Wherever possible, the reporting Investigator uses the clinical rather than the laboratory term (eg, anemia versus low hemoglobin value). In the absence of clinical signs or symptoms, clinically relevant deteriorations in non-mandated parameters should be reported as AEs.

Deterioration of a laboratory value that is unequivocally due to disease progression should not be reported as an AE/SAE.

Any new or aggravated clinically relevant abnormal medical finding at a physical examination as compared with the baseline assessment will be reported as an AE.

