### **8.3.9 Disease progression**

Disease progression can be considered as a worsening of a patient's condition attributable to the disease for which the IP is being studied. It may be an increase in the severity of the disease under study and/or increases in the symptoms of the disease. The development of new or progression of existing metastasis to the primary cancer under study should be considered as disease progression and not an AE. Events that are unequivocally due to disease progression should not be reported as an AE during the study.

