## 9.2 Sample size determination

The study is sized to characterize the PFS benefit of durvalumab in combination with olaparib versus durvalumab monotherapy in first-line patients with unresectable Stage IV UC.

Approximately 150 patients globally will be randomized in a 1:1 ratio to either the durvalumab + olaparib treatment group or the durvalumab + placebo treatment group, 75 patients per arm. The randomization will be stratified based on HRR status (mutant versus wild type) and Bajorin risk index (0 versus 1 versus 2).

The DCO for the primary analysis of PFS will occur when approximately 118 PFS events have occurred across both treatment groups (79% maturity). Assuming a median survival of 3 months for durvalumab monotherapy and recruitment of 150 patients in 6 months, it is estimated that this DCO will occur 7 months following recruitment of the last patient.

If the true PFS hazard ratio (HR) is 0.55 (likely to correspond to an 82% prolongation of PFS), the study will have 90% power to demonstrate a statistically significant difference for PFS at the 2-sided 5% significance level.

The smallest treatment difference that could be statistically significant at the primary analysis of PFS is an HR of 0.69 (assuming a 2-sided p-value of 0.5).

There will be up to 2 analysis timepoints for OS. The first OS analysis will occur at the same time as the primary PFS analysis and will be based on an estimated 44 OS events across therapies (29% maturity), and the second OS analysis will occur when

approximately 100 OS events have occurred (67% maturity). With an approximate 6-month recruitment period and an assumed median OS of 16 months in the durvalumab + placebo arm, it is anticipated that the final analysis will be performed at approximately 27 months after the last patient has been recruited.

Assuming the true OS HR is 0.75, the study will have 30% power to demonstrate a statistically significant OS effect with a 5% 2-sided significance level, allowing for 2 analyses of the data. The smallest treatment difference at the second analysis of OS that could be statistically significant is an HR of 0.68.

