#### **9.4.1.2 Calculation or derivation of safety variables**

##### **Adverse events**

Data from all cycles of treatment will be combined in the presentation of safety data. AEs (both in terms of Medical Dictionary for Regulatory Activities [MedDRA] preferred term and CTCAE grade) will be listed individually by patient.

Any AE occurring before treatment with IP will be included in the data listings but will not be included in the summary tables of AEs. AEs observed up until 90 days following discontinuation of the immunotherapy agents (ie, the last dose of durvalumab +olaprib or durvalumab + placebo) or until the initiation of the first subsequent therapy following discontinuation of treatment (whichever occurs first) will be used for the reporting of the AE summary tables. Further details will be provided in the SAP. Any AE that occurs after a patient has received further therapy for cancer (following discontinuation of IP) will be flagged in the data listings.

A separate data listing of AEs occurring more than 90 days post-last dose of the latest IP will be produced. These events will not be included in the AE summaries.

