### **9.4.3 Safety analyses**

Safety and tolerability data will be presented by treatment arm using the safety population.

Data from all cycles of treatment will be combined in the presentation of safety data. AEs (both in terms of MedDRA preferred terms and CTCAE grade) will be listed individually by patient. The number and percentage of patients experiencing each AE will be summarized by treatment arm and CTCAE grade. Additionally, data presentations of the rate of AEs per person-years at risk may be produced. Any safety summaries examining retreatment with durvalumab will be produced separately as described in the SAP.

Other safety data will be assessed in terms of physical examination, serum chemistry, hematology, vital signs, and ECGs. Exposure to study treatment, time on study, dose delays, and dose reductions will also be summarized. At the end of the study, appropriate summaries of all safety data will be produced, as defined in the SAP.

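### Section 8.2.5 requires every significant ECOG change to be reported as an AE and Section 8.3.9 excludes events unequivocally due to progression, so sites have two opposite instructions for a decline clearly caused by progression

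*Protocol*

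**What the plan says.** - Section 8.2.5, after the ECOG scale: "Any significant change from baseline or screening must be reported as an AE". It does not define a significant change, makes no exception and does not refer to Section 8.3.
- Section 8.3.9: "Disease progression can be considered as a worsening of a patient's condition attributable to the disease for which the IP is being studied". The section also counts increased symptoms of the disease as progression, and ends: "Events that are unequivocally due to disease progression should not be reported as an AE during the study".
- Section 8.3.7 has the matching exemption for laboratory data: "Deterioration of a laboratory value that is unequivocally due to disease progression should not be reported as an AE/SAE". Section 8.3.11 likewise keeps deaths clearly resulting from progression out of SAE reporting.
- Table 1 schedules ECOG at screening, at every cycle and at end of treatment. After treatment, Table 2 schedules it as follows: "At timepoints consistent with tumor assessments; at 30, 60, and 90 days; and then at initiation of subsequent anticancer therapy".
- Section 9.4.1.2 defines what enters the AE summary tables: "AEs observed up until 90 days following discontinuation of the immunotherapy agents", or until the first subsequent therapy if that comes sooner.
- Section 9.4.3: "The number and percentage of patients experiencing each AE will be summarized by treatment arm and CTCAE grade".

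**The concern.** A fall in performance status is one of the ordinary ways in which progression of this disease shows itself. Appendix F makes the link itself: its criteria for treating beyond RECIST progression pair clinically significant progression with an ECOG decline of more than 1. The conflict therefore falls on an event that sites will meet often.

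Two things are at stake. First, if sites follow Section 8.2.5 as written, progression is counted in the AE data as well as in PFS. The plan expects the control arm to progress sooner, so that arm would collect more of these entries without any difference in tolerability. Blinding does not prevent this, because the imbalance comes from the progression rates and not from knowledge of the arm. Second, if some sites follow Section 8.2.5 and others Section 8.3.9, the recorded rate of this AE depends partly on which rule the site chose.

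**Working it through.** **The two rules side by side**

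| ECOG worsening | Section 8.2.5 | Section 8.3.9 |
|---|---|---|
| Significant, not due to progression | AE | AE not excluded |
| Significant, possibly due to progression | AE | AE not excluded |
| Significant, unequivocally due to progression | AE | Not an AE |

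The rules collide only in the last row. Neither section refers to the other. The neighbouring safety sections do hand over to the AE rules: laboratory tests (8.2.1), physical examination (8.2.2) and ECG (8.2.4) point to Section 8.3.7, and vital signs (8.2.3) to Section 8.3.6. Section 8.2.5 does not.

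**Can these declines reach the AE tables?** Yes. ECOG is scored on treatment and up to 90 days after it, and AEs are tabulated over the same period, cut short only by a subsequent therapy.

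**How different are the arms expected to be in progression?** Inputs from Section 9.2: 75 patients per arm, control median PFS 3 months, HR 0.55, recruitment R = 6 months, cut-off F = 7 months after the last patient, 118 PFS events, 90% power, 2-sided 5%.

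1. The plan's own figure first. Schoenfeld power: (√118 / 2) × |ln 0.55| − 1.960 = 5.431 × 0.598 − 1.960 = 1.287, and Φ(1.287) = 0.901. The stated 90% reproduces.
2. Hazards, taking PFS as exponential: control ln 2 / 3 = 0.23105 per month; combination 0.55 × 0.23105 = 0.12708 (median 5.45 months).
3. Probability of a PFS event by the cut-off with uniform accrual: 1 − [exp(−λF) − exp(−λ(R+F))] / (λR).
   - Control: 1 − (0.19843 − 0.04961) / 1.38629 = 0.893, or 66.9 of 75.
   - Combination: 1 − (0.41085 − 0.19167) / 0.76246 = 0.713, or 53.4 of 75.
   - Total 120.4, in line with the planned 118.
4. Difference in PFS events at the cut-off: 89.3% − 71.3% = 18.0 points.
5. Let f be the share of PFS events that carry a significant ECOG decline reported as an AE. The protocol gives no value, so f is an assumption.

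| f (assumed) | Control | Combination | Difference |
|---|---|---|---|
| 10% | 8.9% | 7.1% | 1.8 points |
| 25% | 22.3% | 17.8% | 4.5 points |
| 50% | 44.6% | 35.6% | 9.0 points |

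Read at a fixed 6 months after randomization, the PFS event rates are 75.0% and 53.3%, and the same shares give 2.2, 5.4 and 10.8 points.

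For any given f these figures lie on the high side. PFS events include deaths. Some RECIST progressions occur in clinically stable patients, whom the protocol allows to continue treatment. Declines after a subsequent therapy has started are not tabulated.

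**The case against.** The best defence is that the sections are rule and exception. Section 8.3 governs AE collection, its opening requires staff to know it, and Section 8.3.9 exempts progression without limiting the data source. Section 8.3.7 supports this: its sentence on physical examination findings has no progression exemption either, yet Section 8.3.9 evidently still applies. This reading is plausible and is probably what was intended. But the protocol does not state it, Section 8.2.5 uses mandatory wording, and it is the one section among its neighbours that does not hand over to Section 8.3. A site that follows it literally is not in breach of anything in that section.

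The other side is right on several inferences that a reader might draw:

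- *That an ECOG improvement would also be an AE, because the text says change.* Appendix B 1 defines an AE as an untoward, unfavorable occurrence, so only worsening can qualify.
- *That Section 8.3.9 removes every decline seen at progression.* It covers only unequivocal cases. Doubtful ones are reportable under both sections.
- *That added olaparib toxicity would be masked.* AEs are tabulated by individual term, so a performance-status entry leaves the rates of anemia, nausea and other events unchanged. An any-AE total moves only for patients with no other AE, and a total by worst grade only where this entry is the worst.
- *That a measured bias has been shown.* The shares are assumed, the gap exists only if the planned HR is true, and safety is summarized descriptively without formal testing.

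**Conclusion.** The contradiction stands, and it needs no calculation: for an ECOG decline unequivocally due to progression, Sections 8.2.5 and 8.3.9 give opposite instructions. Section 8.2.5 is the outlier against the principle that the protocol applies in Sections 8.3.7, 8.3.9 and 8.3.11.

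The consequence is limited. Literal use of Section 8.2.5 would add performance-status AEs roughly in proportion to progression, and sites may differ. This touches that one term and the any-AE or grade totals. The size cannot be derived from the documents. The illustrative 1.8 to 9.0 points at the cut-off rests on exponential PFS, the planned HR of 0.55, an assumed 10% to 50% of PFS events with such a decline, and reporting of every one. The primary PFS analysis, the sample size and the alpha are unaffected. It is a reporting rule that is wrong as written, worth correcting because it decides what enters the AE tables.

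**What to change.** Reconcile the two passages by amending Section 8.2.5 so that a significant worsening of ECOG performance status from baseline or screening is reported as an AE unless it is unequivocally due to disease progression, with a cross-reference to Section 8.3.9. ECOG is already a safety variable in its own right (Table 3 and Table 15) and continues to be summarized separately, so declines due to progression remain visible.

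The cost is a one-sentence protocol change and a reminder to sites. The sentence does not define a significant worsening, so some variation between sites will remain unless the reminder also says what is meant.
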